5.2. Sensitivity analyses

Four sensitivity analyses are planned:

- 1. The analysis described above will be repeated using multiple imputation, if more than 10% of outcome data is missing.
- 2. The analysis described above willbe repeated without the covariates participant age, inhaled steroid use at baseline, days since symptom onset at randomisation, whether there are children in the household and household size.
- 3. The algorithm to determine SARS-CoV-2 infection will be changed by deeming all inconclusive results (including on Day 0) to be positive, using only healthcare provider collected swabs.
- 4. The algorithm to determine SARS-CoV-2 infection will be changed by deeming all inconclusive results (including on Day 0) to be negative, using only healthcare provider collected swabs.

5.3. Supplementary analyses

We define a supplementary estimand, through handing the intercurrent event of not taking study drug differently.

Supplementary estimand

Population: Household contacts who test negative for SARS CoV-2 on day 1 (baseline) PCR testing using the health care provider swabs

Treatment: Unfractionated intranasal heparin 1400u each nostril (as heparin solution 5,000u/ml, 140microL/actuation, TWO actuations each nostril) THREE times daily via a plastic nasal inhalator device or saline control

Outcome: Testing positive for SARS-CoV-2 by PCR on any of three health care provider collected swabs at days 3, 5 and 10 while participant and index case do not discontinue treatment due to adverse events. The algorithm to determine SARS-CoV-2 positivity is described in detail in Section 3.8. If one of the post-baseline swabs is missing, but all observed swabs were negative, the participant will be regarded to be negative. If more than one post-baseline swab is missing and the observed swabs were all negative, the outcome will be regarded to be missing.

Summary measure: Both relative (risk ratio) and absolute differences (risk difference) in proportions will be reported with 95% confidence intervals

Potential intercurrent events:

Index case in the household not taking study drug. This is defined as compliance <90% Participant (this household member) not taking study drug. This is defined as compliance <90% Either participant (this household member) or index case stop treatment due to adverse event Participant hospitalisation during first 10 days (removed from household) Participant received an anti-viral

Strategy for handling intercurrent event:

Index case in the household not taking study drug. This is defined as compliance <90%: This intercurrent event will be handled following the hypothetical strategy. For index cases who used <90% of study drugs we will set all SARS-CoV2 infections observed in the household to missing. We will use multiple imputation to impute these outcomes.

Participant (this household member) not taking study drug. This is defined as compliance <90%: This intercurrent event will be handled following the hypothetical strategy. We will set all SARS-CoV2 infections observed to missing. We will use multiple imputation to impute these outcomes. Either participant (this household member) or index case stop treatment due to adverse event: We will handle this intercurrent event using the while on treatment strategy. We will do this by excluding outcomes after participants stop study treatment due to adverse events from the analysis. All other intercurrent events will be handled by using the treatment policy strategy, which means that those intercurrent events will be ignored.

This analysis will only be done if more than 7% of participants had the intercurrent events.

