3.7. Handling of missing data

If less than 10% of data is missing, the primary analysis will be conducted using the participants with available data for each outcome. However, if there are >10% missing data in the primary or secondary outcomes, we will conduct the analysis under a plausible assumption regarding the missingness mechanism that will be guided using expert clinical knowledge prior to observing the data, which will be determined by generating directed acyclic graphs. We suspect that the data will be recoverable (that is able to be estimated without bias from the observed data alone), and multiple imputation will be used to handle the missing data in all

outcomes. Imputations will be generated using chained equations, also known as fully conditional specification, with 50 imputed datasets and 10 iterations between each imputation. Ideally this would be conducted using a single regression model for all outcomes, although it may be necessary to impute incomplete outcomes using separate models. Imputation will be carried out separately by arm, to ensure that any treatment effects are maintained. Baseline characteristics as well as any variables that are predictors of missingness and/or associated with the incomplete outcomes will be included as auxiliary variables in the imputation model. Estimates of interest will be obtained using Rubin's rules, and will be reported with 95% confidence intervals and *p*-values.

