4.4. Compliance

Participants will be asked about compliance and symptoms daily. Parents will act as a proxy for children <16 years old. They will be asked how many doses they have used in the previous day. We will provide the number of participants who took 0, 1, 2 or 3 doses per day for 10 days.

We will also calculate the percentage of prescribed study dose that was taken. Each participant should take 3 doses per day, 30 doses over the 10 days. Participants could start the study late on the first day, in which case one would expect them to only have used 1 or 2 doses, instead of 3. Starting late on the first day would also distort reporting of study compliance on Day 2, since we ask "how many doses of study drug have you taken in the last 24 hours". We do not have the time of day when the study was started and thus cannot determine how many doses a participant should have used on the first or second day. For this reason, we will exclude Days 1 and 2 from the calculation of compliance. Thus, the percentage compliance will be calculated as (number of doses taken from days 3 to 10/24) multiplied by 100. If compliance data is missing for a day, the denominator will be reduced by 3. The mean percentage compliance will be summarised. All compliance summaries will be provided in each treatment arm as well as for participants who were positive and negative for COVID-19 at baseline by treatment arm.

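### As worded, SAP Section 5.3 sets only observed infections to missing when compliance is under 90%, not the same people's negative results, which would lower both arms' risks in the supplementary estimand

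*SAP*

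**What the plan says.** Section 5.3 defines a supplementary estimand that differs from the primary one in how it treats not taking study drug. Compliance below 90%, by the index case or by the participant, is assigned a hypothetical strategy. For the index case the data step is: "For index cases who used <90% of study drugs we will set all SARS-CoV2 infections observed in the household to missing". For the participant it is: "We will set all SARS-CoV2 infections observed to missing". In both places the next sentence says that multiple imputation will be used and calls the imputed values outcomes.

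Stopping because of an adverse event is a separate intercurrent event with a while-on-treatment strategy. It is written into the outcome definition ("while participant and index case do not discontinue treatment due to adverse events") and carried out by "excluding outcomes after participants stop study treatment due to adverse events from the analysis".

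Other provisions that bear on the point:
- Section 5.3, outcome: "If one of the post-baseline swabs is missing, but all observed swabs were negative, the participant will be regarded to be negative".
- Section 5.3, trigger: "This analysis will only be done if more than 7% of participants had the intercurrent events".
- Section 3.7, the only imputation method described: imputation is done separately by arm, and "any variables that are predictors of missingness and/or associated with the incomplete outcomes will be included as auxiliary variables in the imputation model". Compliance is not named.
- Section 4.4: "the percentage compliance will be calculated as (number of doses taken from days 3 to 10/24) multiplied by 100". A day without compliance data takes 3 off the denominator.
- Section 6.1 applies the same supplementary analysis to Measures 1.1 to 1.3.

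**The concern.** A hypothetical strategy asks what would have happened had the drug been taken. For people who did not take it, neither a positive nor a negative result answers that, so both should be set aside. The text removes infections and is silent on negatives. A programmer who follows it would delete the positives of non-adherent people and keep their negatives. Whether a value is missing then depends on the value itself, and imputation from the remaining data cannot restore what was removed.

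The result is planned for the hypothetical-estimand rows of Table 8, beside the primary result, and of Table 10. It is the plan's estimate of the effect when drug is taken, so it would be read closely if adherence turned out poor.

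**Working it through.** **Inputs.** Design attack rates are 85% control and 75% intervention (Section 2.6). Section 5.3 states no figure to reproduce, but these rates do underlie the sample size: 250 per arm × design effect 1.4 (1 + 2 × 0.2) ÷ 3 contacts = 117 households per arm, close to the stated 120, and 120 ÷ 0.9 = 134. The share d of day-1-negative contacts affected by their own or the index case's compliance below 90% is not in the SAP. I assume 7% to 20%, unrelated to infection. The 7% trigger counts people with the intercurrent events, so it is only a convenient lower end and does not anchor d.

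**Rule as worded, compliance not in the imputation model.** In an arm with true risk p, a share dp is deleted (positives among the affected). What remains is (1−d)p positives out of 1−dp. Imputing by arm fills the gap at that observed rate, so the estimate is (1−d)p/(1−dp) and the downward bias is dp(1−p)/(1−dp).

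**Rule as worded, compliance in the model.** Everyone affected with an observed result is negative, so imputed values tend to negative. The estimate falls to as low as (1−d)p, a bias of up to dp.

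| d (both arms) | Compliance in model | Control (true 85%) | Heparin (true 75%) | Difference (true 10.0) | RR (true 0.882) |
|---|---|---|---|---|---|
| 7% | no | 0.7905/0.9405 = 84.1% | 0.6975/0.9475 = 73.6% | 10.4 | 0.876 |
| 20% | no | 0.680/0.830 = 81.9% | 0.600/0.850 = 70.6% | 11.3 | 0.862 |
| 7% | yes (limit) | 79.1% | 69.8% | 9.3 | 0.882 |
| 20% | yes (limit) | 68.0% | 60.0% | 8.0 | 0.882 |

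**No true effect, 85% in both arms.** With equal d the two arms shift alike and no difference appears. With 10% affected on placebo and 20% on heparin, the estimates are 83.6% and 81.9%, a spurious benefit of 1.7 points; with compliance in the model the limit is 76.5% − 68.0% = 8.5 points. Reversing the imbalance gives a false harm of the same size.

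**Simulation check** (2,000,000 per cell, d = 20%, adherence independent of infection). True 85% gives 81.9% as worded, 68.0% with compliance in the model, and 85.0% when positives and negatives are both set to missing. True 75% gives 70.6%, 60.0% and 75.0%.

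**Overlap with adverse-event stops.** 90% of 24 doses is 21.6, so 21 doses (87.5%) is below the limit. A stop at the end of day 8, with later days recorded as zero, scores at most 18/24 = 75% if diary entries cover the same day, or 21/24 = 87.5% if they cover the previous day. Both strategies then apply. If the later days are missing instead, the score can be 18/18 or 21/21 = 100%. No sentence says which strategy takes precedence.

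**The case against.** The strongest reply is that the text means infection status. The sentence after each rule speaks of imputing outcomes, Section 3.8 is about assigning infection status, Section 5.1 models infection status as the binary outcome, and keeping only negatives would contradict the declared hypothetical strategy. That reading is plausible, and a reader should not infer that the sponsor intends to delete positives only. It does not settle the matter: the data step names infections, the adverse-event rule in the same section uses the wider term, and no other section says the negatives go too. The two readings give different numbers.

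The larger figures are also conditional. A reader might infer that a false treatment effect is likely. The documents do not support that: it needs an imbalance in adherence between arms, which is assumed here, in a trial described as double blind. The 68% and 8.5-point figures further need compliance in the imputation model. Section 3.7 allows this without naming it, and an analyst might notice that the indicator separates the outcome perfectly. Nor is every contrast distorted when adherence is equal: with compliance in the model, the risk ratio at equal d is unchanged.

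The remedy is not free of assumptions either. Compliance is measured over days 3 to 10 and may respond to an early positive. If, as an illustration, 20% of infected and 5% of uninfected people fall below 90% at p = 85%, setting all results to missing gives 0.68/0.8225 = 82.7%, against 0.68/0.83 = 81.9% as worded. Most of the bias stays.

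For Measures 1.1 to 1.3 the wording fits less well, because that population is already infected on day 1. The SAP gives no rates there, so I attach no size.

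Finally, the overlap might be read as an error. It shows no wrong result; a reasonable reader could give the adverse-event rule priority. It is a request for clarification.

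**Conclusion.** The point holds for the wording of the data step. Followed as written, Section 5.3 makes missingness depend on the outcome and lowers each arm's estimated risk: by about 1 to 3 points at an 85% rate for d of 7% to 20% without compliance in the imputation model, and by up to dp with it. At the design rates and equal d, the 10-point difference becomes 10.4 to 11.3 points, or as little as 9.3 to 8.0 with compliance in the model, where the risk ratio is unchanged. These sizes rest on an assumed d and on adherence unrelated to infection.

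The scope is the supplementary estimand, run only if its trigger is met, and its reuse for Measures 1.1 to 1.3. Nothing here casts doubt on the primary treatment-policy analysis, which ignores these events. The change is worth making because it is small and the present text can be programmed in two ways.

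**What to change.** In Section 5.3, state that for anyone with the under-90% event, own or index case, the whole infection outcome over days 3, 5 and 10, positive or negative, is set to missing before imputation. State also that such people are not scored negative again through the one-missing-swab rule. Leave the under-90% indicator out of that imputation model: once every outcome in the group is missing, the data hold nothing from which to estimate its effect. State how the rule applies to the single-day outcomes of Measures 1.1 to 1.3.

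As a secondary clarification, say which strategy applies when an adverse-event stop also meets the under-90% event, and how diary days after the stop count towards compliance.

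The cost is two or three sentences and one reprogrammed derived variable, with no new data collection. The drawbacks should be acknowledged in the text: more outcomes are imputed, swabs taken before adherence lapsed are discarded, and the result is valid only if non-adherence is unrelated to infection given the variables in the imputation model.

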The same analysis as described in Section 5.1 for the primary outcome will be done. We will do the same sensitivity and supplementary analysis, but no subgroup analyses are planned.

Measure

1.4. Time to swab negative based on health care provider collected nasal swab for household members index cases and household contacts) who were swab positive on day 1 by PCR

Estimand

Population: Household members who tested positive for SARS CoV-2 on day 1 on a nasopharyngeal swab PCR **Treatment**: Initially randomised intervention to unfractionated intranasal heparin 1400u each nostril (as heparin solution 5,000u/ml, 140microL/actuation, TWO actuations each nostril) THREE times daily via a plastic nasal inhalator device or saline control and any subsequent deviations to the per protocol use of the intervention over 10 days

Outcome: Days from randomisation to the date of the first negative nasal swab. Participants who still test positive on day 10 will be censored on day 10 and regarded as not testing negative.

Summary measure: Median time to first negative test in each treatment arm. Hazard ratio.

Potential intercurrent events:

Index case in the household not taking study drug. This is defined as compliance <90% Participant (this household member) not taking study drug. This is defined as compliance <90% Either participant (this household member) or index case stop treatment due to adverse event Participant hospitalisation during first 10 days (removed from household) Participant received an anti-viral

Strategy for handling intercurrent event:

All intercurrent events will be handled through the treatment policy strategy, which means that the intercurrent events will be ignored.

Days to first negative test will be calculated from baseline to the first negative PCR tests within the first 10 days after randomisation. Participants who still test positive at the last time point will be censored at the time

of last test. Participants who are lost to follow-up without testing negative, will be censored at the time of the last positive test. The days to negative test will be compared between the two treatment arms using a proportional hazards models with clustered standard errors [using vce(cluster) in Stata]. The model will be adjusted for the same set of defined baseline covariates (Section 5.1). Days to negative test will be summarised by reporting the median, with 95% confidence interval.

Measure

1.5 Mean Ct values on days 3, 5 and 10

Estimand

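### The supplementary estimand sets day 3 and day 5 infections to missing because of doses missed after the positive swab

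*SAP*

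**What the plan says.** Section 4.4 of the SAP holds its only compliance formula: "the percentage compliance will be calculated as (number of doses taken from days 3 to 10/24) multiplied by 100". The first two days are left out ("we will exclude Days 1 and 2 from the calculation of compliance") because the time of day of the first dose was not recorded. A day without a report lowers the denominator: "If compliance data is missing for a day, the denominator will be reduced by 3".

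Section 5.3 defines not taking study drug as compliance below 90% and handles it by a hypothetical strategy. For the participant: "This intercurrent event will be handled following the hypothetical strategy. We will set all SARS-CoV2 infections observed to missing". For the index case: "For index cases who used <90% of study drugs we will set all SARS-CoV2 infections observed in the household to missing". The deleted outcomes are multiply imputed. Neither rule mentions when the doses were missed relative to the infection.

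The same section does respect time order for stopping because of an adverse event: there, only outcomes after the stop are excluded. The supplementary analysis runs only if more than 7% of participants have the intercurrent events. Section 6.1 carries it over to Measures 1.1 to 1.3: "We will do the same sensitivity and supplementary analysis, but no subgroup analyses are planned".

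**The concern.** Doses missed after an infection has been detected cannot have contributed to that infection. A hypothetical strategy for not taking the drug should therefore act on outcomes that follow the missed doses. Section 5.3 instead applies a whole-course score to an outcome that may already be settled on day 3 or day 5.

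Infection may itself change later dosing, for instance through illness. Infected people would then be flagged more often than uninfected people, and valid positives would be removed selectively. The index-case rule reaches further, because one person's late lapse voids every infection already seen in the household. At stake are the hypothetical-estimand rows of Tables 8 and 10. The 7% trigger is also affected, since it counts the same events.

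**Working it through.** **Inputs.** Compliance formula and dose counts: Section 4.4. The 90% threshold: Section 5.3. Swabs on days 3, 5 and 10, each +/- 1 day: Section 2.7. Risks of 85% and 75%: Section 2.6. The SAP gives no missed-dose or lapse rates, so those below are assumptions.

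**1. The plan's figure.** Days 3 to 10 are 8 days; 8 x 3 = 24 doses, as stated, out of 30 prescribed.

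**2. What triggers the event.** 0.90 x 24 = 21.6. With complete reports, 22/24 = 91.7% passes and 21/24 = 87.5% fails. Three missed doses, the equivalent of one day, are enough.

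**3. Share of the score after the swab.** Doses after a swab on day d = 3 x (10 - d), capped at 24, with all doses on the swab day counted as before it.

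| Swab | Nominal day | Across the +/- 1 day window |
|---|---|---|
| Day 3 | 21/24 = 87.5% | 75% (taken day 4) to 100% (taken day 2) |
| Day 5 | 15/24 = 62.5% | 50% (taken day 6) to 75% (taken day 4) |
| Day 10 | 0/24 | at most 3/24 = 12.5% (taken day 9) |

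Someone who takes every dose up to a nominal day 3 positive and then stops scores 3/24 = 12.5%. After a day 5 positive the score is 9/24 = 37.5%. Both infections are set to missing. Conversely, someone who takes nothing on days 1 and 2 and everything afterwards scores 24/24 = 100%, having taken 24/30 = 80% of the prescribed doses.

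**4. How easily it happens.** Assume each later dose is missed independently with probability 5%, 10% or 20%. The chance of three or more misses is 8.5%, 35% or 82% over the 21 doses after a day 3 positive, and 3.6%, 18% or 60% over the 15 doses after a day 5 positive.

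**5. Effect on the estimate, all outcomes of flagged people blanked.** Let p be the true risk, q1 the flagged share of infected people and q0 = 0.10 that of uninfected people. If imputation returns the risk seen in unflagged people of the same arm, the estimated risk is p(1 - q1) / [p(1 - q1) + (1 - p)(1 - q0)].

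- q1 = 0.25, p = 0.85: 0.6375/0.7725 = 82.5%.
- q1 = 0.25, p = 0.75: 0.5625/0.7875 = 71.4%.
- q1 = 0.10: the risk is unchanged.

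| q1 heparin | q1 placebo | Heparin | Placebo | Difference (true -10) |
|---|---|---|---|---|
| 25% | 25% | 71.4% | 82.5% | -11.1 |
| 25% | 10% | 71.4% | 85.0% | -13.6 |
| 10% | 25% | 75.0% | 82.5% | -7.5 |

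With no true effect (85% in both arms), the two unequal patterns give -2.5 and +2.5 points.

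**6. Effect on the literal wording, only infections blanked.** With a share f of infections flagged and negatives kept, the estimated risk is p(1 - f)/(1 - pf). For f = 0.20: 0.68/0.83 = 81.9% and 0.60/0.85 = 70.6%. Here risks fall even if infected and uninfected people lapse equally often.

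**The case against.** The strongest reply is that little depends on this. The primary estimand follows a treatment-policy strategy, and the affected analysis is supplementary and conditional on the 7% trigger. Under the formula in step 5, nothing is distorted if infected and uninfected people lapse equally often. Section 3.7 also puts baseline and auxiliary variables into the imputation model, which could recover part of what is deleted. All of this stands as a limit on consequence. None of it makes it right to delete an observed infection because of later dosing, and equal lapse rates do not help if the rule is applied literally (step 6).

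Three stronger readings are tempting and unsupported.

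- A reader might infer that fully dosed people lose their infections. Anyone fully dosed on days 3 to 10 scores 24/24 and is kept. Those affected were fully dosed only up to the swab.
- A reader might infer that nearly all of the score follows the outcome. That is fair for day 3. For day 5, including Measure 1.2, the share is 62.5% at the nominal day and 50% if the swab is taken on day 6. For a first positive on day 10 the problem essentially does not arise.
- A reader might infer that the rule favours heparin. Section 2.5 describes a double-blind trial with a matching comparator, and the SAP gives no reason to expect more lapse after infection on heparin. It also does not say that participants learned their PCR results while dosing. The reversed split attenuates the effect.

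A simple cut-off at the first positive swab would not be a clean remedy. Uninfected people would still be scored over the whole course and removed preferentially. With q1 = 0 and q0 = 0.10, the risks become 0.85/0.985 = 86.3% and 0.75/0.975 = 76.9%, a difference of -9.4 points.

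**Conclusion.** The point holds. Section 5.3 is a wrong rule as written, not merely a missing detail: it deletes valid day 3 and day 5 infections because of later dosing, and it conflicts with the time-ordered handling of adverse-event stops in the same section. The link to Section 4.4 is an inference, since Section 5.3 does not cite it, but the SAP contains no other compliance formula.

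The dose shares follow from the SAP alone. The size of the bias does not. Under the assumed lapse rates it is about 1 point on the risk difference when the arms lapse alike, and about 2.5 to 3.6 points in either direction when they differ. It is confined to the supplementary estimand and its reuse for Measures 1.1 to 1.3. The change should be made before those analyses are run.

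**What to change.** In Section 5.3, and where Section 6.1 reuses it, apply the non-compliance event in time order, for participant and index case alike:

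- Judge compliance cumulatively up to each swab from the daily reports.
- Keep every swab result obtained before non-compliance begins, including any infection already observed.
- Set to missing only swab results after it begins, positive and negative alike, and impute them conditional on the earlier swab results.
- State that doses missed after the first positive swab do not void that infection. For Measures 1.1 to 1.3, where everyone is positive on day 1, say the same of doses missed after the swab being analysed.
- State that swabs blanked in this way are imputed, and are not covered by the existing rule that scores a participant with one missing swab and otherwise negative results as negative.

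The cost is SAP wording and a date-limited compliance variable built from daily reports already collected. The drawback is a coarse score before the day 3 swab. It rests on few doses, and the expected counts for days 1 and 2 are uncertain because the start time was not recorded. The SAP should say how those two days are counted.

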2.7 Study procedures

When a participant is confirmed to be SARS-CoV-2 positive all consenting household members are enrolled and randomised to the same treatment arm. All consenting household members 5 years of age and older will be given the same study treatment. Treatment is 10 days and follow up for primary outcome is 10 days. Follow up for some secondary outcomes are 28 days and outcomes related to long COVID is 6 and 12 months post randomisation.

Daily communication via SMS, online or phone will be conducted by a research team member who will be trained in standard operating procedures as per trial manual. Paediatric or adult swabs (Rhinomed) will be provided to all participants with detailed instructions for self-collection and storage until collected by a research team member. Health care provider collected PCR nasopharyngeal swabs will be collected from all participants prior to commencement of study medication and on day 3, 5 and 10 (+/- 1 day for all time points).

Phone call follow up at day 14 and 28 by a research team member will assess which participants became symptomatic after the initial treatment period and whether participants required hospitalisation during that time. Detailed medical information as to reasons for hospital admission will be sought to confirm if admission was related to COVID-19 infection or for alternative reasons. Research team members will be trained specifically in questions to ask according to trial manual, which will include an escalation process if a research team member believes that additional clinical care is required for the participant or family member.

Telemedicine follow up at day 180 +/- 10 days and day 365 +/- 10 days to ascertain any evidence of long COVID neurological symptoms.

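### Supplementary estimand (SAP Section 5.3): read literally, the missing-swab rule or the compliance rule replaces the while-on-treatment outcome for adverse-event stops between the day 3 and day 5 swabs

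*SAP*

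**What the plan says.** All of this stands in SAP Section 5.3 unless noted.

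- **Outcome.** A positive day 3, 5 or 10 swab counts "while participant and index case do not discontinue treatment due to adverse events".
- **Missing swabs.** The two rules of the primary estimand (Section 5.1) are repeated without change: "If one of the post-baseline swabs is missing, but all observed swabs were negative, the participant will be regarded to be negative". And: "If more than one post-baseline swab is missing and the observed swabs were all negative, the outcome will be regarded to be missing".
- **Adverse-event stop by the participant or the index case.** "We will handle this intercurrent event using the while on treatment strategy", carried out as follows: "We will do this by excluding outcomes after participants stop study treatment due to adverse events from the analysis".
- **Participant compliance below 90%.** The hypothetical strategy applies: "We will set all SARS-CoV2 infections observed to missing", followed by multiple imputation. If the index case is below 90%, the same is done for the infections in the household.
- **Compliance** (Section 4.4) is doses taken on days 3 to 10 divided by 24. The denominator falls by 3 for each day without data.
- **Trigger.** The analysis is run only if more than 7% of participants had the intercurrent events.

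The SAP does not say whether a swab excluded because of a stop is a missing swab, what the outcome is if no swab precedes the stop, or which rule governs when a stop for an adverse event also brings compliance below 90%.

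**The concern.** A while-on-treatment outcome asks whether infection was seen up to the stop. For someone with a negative day 3 swab who stops on day 4, the answer is no, and it has been observed. The missing-swab rules were written for the primary estimand, where an absent swab is lost information. Here two swabs are absent by design. If the rules do not distinguish the two cases, whether a stopper's outcome is kept depends on the outcome itself: the day 3 negative drops out and the day 3 positive may stay.

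Imputing the dropped outcomes would estimate what would have happened without stopping. That is the hypothetical strategy, not the one named. Two programmers working from this text could compute different estimands.

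**Working it through.** **Step 1: the rules by time of stop.** This assumes nominal swab days, no swab uncollected, a swab on the day of the stop counted as on treatment, and excluded swabs counted as missing.

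| Stop | Swabs left | All left negative | Any left positive | While-on-treatment answer if negative |
|---|---|---|---|---|
| Before the day 3 swab | none | missing | none possible | not observed |
| From the day 3 swab to before the day 5 swab | day 3 | **missing** | positive | **negative** |
| From the day 5 swab to before the day 10 swab | days 3, 5 | negative | positive | negative |
| From the day 10 swab on | all | negative | positive | negative |

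Only the second row departs from the named strategy. Each swab has a window of one day either side (Section 2.7), so the actual cut depends on swab dates.

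**Step 2: overlap with the compliance rule.** If days after the stop count as zero doses, a stop after a full day 3 gives 3/24 = 12.5%, after day 4 gives 6/24 = 25%, and after day 9 gives 21/24 = 87.5%. Every stop up to the end of day 9 is therefore below 90%. If the days after the stop have no data instead, the denominator shrinks: 3/3 or 6/6 = 100%, and only the adverse-event rule applies. So a day 3 positive in the second row is kept on one route and set to missing on the other.

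**Step 3: size if positives are kept and the analysis is complete-case.** The SAP gives no adverse-event stop rates, so those are assumptions. From Section 2.6 come the risks of 75% (heparin) and 85% (control). The sample size built on them reproduces closely: 250 per arm × (1 + 2 × 0.2) / 3 = 116.7, so 117 households per arm against the stated 120.

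Let s be the share of participants affected by a stop in the second-row window, R the risk in those who continue, and r the day 3 risk in those affected.

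- While on treatment: W = (1 − s)R + s·r
- Literal rule: L = W / [(1 − s) + s·r]

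With r = 25% on heparin and 30% on placebo (assumed):

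- s = 5% v 1%. W: 0.7125 + 0.0125 = 0.725 v 0.8415 + 0.003 = 0.8445, difference −12.0 points. L: 0.725/0.9625 = 0.753 v 0.8445/0.993 = 0.850, difference −9.7.
- s = 10% v 2%. W: 0.700 v 0.839, −13.9. L: 0.700/0.925 = 0.757 v 0.839/0.986 = 0.851, −9.4.
- s = 5% in both arms. −9.75 v −9.91, a gap of 0.16.
- s = 10% in both arms. −9.50 v −9.81, a gap of 0.31.

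With r set instead to a fixed share of R, the share of infections already positive on day 3:

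| s (heparin v placebo) | Share by day 3 | W difference | L difference | Gap |
|---|---|---|---|---|
| 5% v 2% | 70% | −10.6 | −9.5 | 1.1 |
| 5% v 2% | 50% | −11.0 | −9.6 | 1.4 |
| 10% v 3% | 50% | −12.5 | −9.2 | 3.3 |
| 7% v 7% | 30% | −9.5 | −9.9 | 0.4 |

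**Step 4: size if positives are set to missing as well.** Before imputation, everyone in the window is then missing, and a complete-case analysis returns 75% v 85%, or −10.0. The pattern that keeps only infected stoppers disappears, but the observed on-treatment answers are discarded for all of them.

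**The case against.** The SAP nowhere states that excluded swabs count as missing, although a reader might infer it. The outcome wording, limited to the time before an adverse-event stop, can be read as placing later swabs outside the outcome, with the missing-swab rules covering only swabs not collected. That stands: this is an unresolved rule whose most literal reading goes wrong, not a stated error.

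Three stronger inferences are also tempting, and the documents do not support them.

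- **That all uninfected people who stop by day 4 are lost while the infected are kept.** Before the day 3 swab nobody is kept, and after it the compliance rule may remove the positives too.
- **That the while-on-treatment strategy is undone altogether.** Stops from the day 5 swab onward lose at most one swab and pass the missing-swab rule as intended.
- **That the estimate is always pulled toward no effect.** With equal stopping in Step 3's first set of inputs it moves slightly the other way. Under unequal stopping it is attenuated relative to the named estimand, whose own value grows with more heparin stops because stoppers are watched for fewer days.

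The overlap with the compliance rule does not rescue the plan. It is a second route by which the named strategy is lost, and no order between the two rules is given.

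It is also fair that the estimand is supplementary and conditional. On the other side, a stop by the index case triggers the event too, so one stop can reclassify every negative contact in a household, and the affected share can exceed the individual stop rate.

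**Conclusion.** The point holds for adverse-event stops, by the participant or the index case, that fall between the day 3 and day 5 swabs. On the literal reading an observed on-treatment negative becomes missing. A day 3 positive is kept or imputed according to a precedence the SAP does not give. On neither route is the while-on-treatment outcome computed for these people.

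If positives are kept and the analysis is complete-case, the risk difference moves by about 1 to 4.5 points when 5% to 10% stop on heparin against 1% to 3% on placebo, and by less than 0.4 point when stopping is equal. These sizes rest on assumed stop rates and day 3 positivity. The planned difference is 10 points.

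The primary estimand handles all these events by treatment policy and is unaffected, and the supplementary analysis runs only above the 7% trigger. The point is therefore worth correcting but does not threaten the main result.

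**What to change.** Add to Section 5.3:

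1. Swabs due after an adverse-event stop by the participant or the index case are outside the outcome and are not counted as missing. Because of the swab window, judge this by actual swab and stop dates.
2. For participants with such a stop, the outcome is positive if any on-treatment swab is positive, negative if at least one on-treatment swab was observed and all observed ones are negative, and missing if none was observed. The last clause matters: without it, someone who stopped before any post-baseline swab would be coded uninfected with no observation.
3. For adverse-event stops the while-on-treatment rule takes precedence. The below-90% compliance rule applies only to non-adherence not due to an adverse event.

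The cost is a few sentences and a change to the derivation. No new data are needed.
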